calculated for the primary endpoint of time to death or hospital re-admission within the 6 month post-discharge period, assuming an alpha level of 0.05, power of 0.80, and a ratio of treatment to placebo random assignment of 1:1. In sub-Saharan Africa, it is estimated that 2-15% of children aged less than 5 years died within 6 months of hospital discharge 15.5% of children who survived discharge from the district hospital re-admitted with the same diagnosis within 6-months[7, 9, 25] Assuming

an additional 5-10% of children are re-admitted for other conditions, we expect that re-hospitalizations will occur in 20.5 to 30.5% of children enrolled in the study. Combined with our expected fatality rate (2-15%), we expect the cumulative incidence of the combined endpoint to range from 22.5 to 45.5%. [25] Based on a previous trial of mass drug administration of a single dose of azithromycin in which a single dose of the antibiotic was associated with a 49% reduction in risk of death, we calculated sample sizes using estimates of reduction in risk ranging from 30-50% with the cumulative incidence range of 22.5 to 45.5%, and found the sample size required ranged from 90 to 550 children per treatment arm.[10] Using the most conservative estimates of a hazard ratio of 0.70 and 22.5% prevalence of re-admission/death, we need to enroll 1100 children in the study (550 per arm) to achieve adequate power. We will recruit an additional 300 children ($\approx 20\%$) to account for possible loss to follow-up, resulting in a total planned enrollment of 1400 children, or 700 per treatment group. When considering mortality alone, and estimated mortality ranges of 2-15%, we will have $>80\%$ power to detect hazard ratios ≤ 0.5 for mortality rates of $\geq 8\%$ and hazard ratios ≤ 0.6 for mortality rates $\geq 11\%$ (Figure 6). Although the ability to determine differences in mortality between arms will require either a high mortality rate or a large measure of effect, in Kenya, re-hospitalization is associated with as much as a 23.6-fold increased risk of death, indicating that this outcome is itself a severe outcome and an intermediate marker of death.[7]

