*Aim 2b. To determine whether empiric administration of azithromycin at hospital discharge increases risk of antimicrobial resistance in commensal *E. coli* and pneumococcal isolates from treated children and their household contacts.* Among children and adult household contacts in whom commensal *E. coli* and/or *S. pneumoniae* are isolated, we will compare the proportion of β -lactam or macrolide resistance, or both, between randomization arms and Contact Cohorts for each arm, at 90-days and 6 months using GEE with a

Poisson link and exchangeable correlation structure. A chi-squared test will be used to determine whether the association between intervention arm and antimicrobial resistance wanes over time. Because the likelihood of having a bacterial pathogen isolated may depend on baseline factors, including intervention arm, we will conduct secondary analyses utilizing propensity scores to account for the potential differential likelihood of having antimicrobial susceptibility testing performed, which will allow us to make inference to the entire study population and their contacts.

Aim 3. To identify correlates and intermediate markers of post-discharge mortality and hospital-readmission among hospitalized Kenyan children. Enrollment hospital admission diagnosis, indicators of malnutrition, age, and randomization arm will be assessed in a multivariable Cox regression model to identify correlates of the primary endpoint of death and/or hospital-readmission independent of the treatment effect. In addition, Cox regression models will also be built for correlates of mortality and correlates of re-admission individually to understand distinct cofactors for each of these outcomes.

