1. Randomly selected adult contacts who are participating in AMR sub-study 2. Random subset of adult AMR sub-study participants in whom S. pneumoniae	Prevalence of resistance to azithromycin. In secondary analyses, prevalence of amoxicillin/ K clavulanate, ampicillin, chloramphenicol, clarithromycin, erythromycin, penicillin, trimethoprim-sulfamethoxazole @ 0, 3, & 6 months	Randomization arm (ITT primary and per-protocol secondary)	1) Site 2) Adjusting for imbalanced baseline factors & baseline presence of resistance 3) Adjusting for propensity score made up of factors predictive of likelihood that S. pneumoniae is isolated	GEE with Poisson link & exchangeable correlation structure. Wald tests to compare between arms and to test for time-interaction (waning in resistance from 3 to 6 months in AZM arm)

Aim 3. To identify correlates and intermediate markers of post-discharge mortality and hospital-readmission among hospitalized Kenyan children.

Population	Dependent variable	Independent Variable(s)	Covariates	Statistical model
All enrolled children	Time to death or re-hospitalization	• Child nutritional status • HIV status (child & mother) • Vaccination status • Abnormal discharge • Discharge diagnosis • Length of hospital admission • Infection presence at discharge • Antibiotic resistance at discharge • Feeding practices • Socio-economic status • Caregiver education and nutritional status	Randomization arm, site	Cox proportional hazards
	Time to re-hospitalization		Randomization arm, site	Cox proportional hazards and Andersen-Gill for >1 hospitalization
	Time to death		Randomization arm, site	Cox proportional hazards

Aim 4. To determine the cost-effectiveness of post-discharge administration of a 5-day course of azithromycin in settings of varying antibiotic use, re-hospitalization rates, and mortality rates.

Costs analysis: We will assess the costs of all supplies, services and equipment necessary to implement the intervention (direct medical costs). The perspective will be that of the healthcare provider, i.e. Kenya's Ministry of Health. Using WHO guidelines and its ingredients approach, we will quantify the resources and associated unit costs required to deliver a 5-day course of azithromycin, organized in Version 5.0

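### Aim 3 uses ordinary Cox regression for time to death, although the planning case implies only about 22-28 deaths; Firth-penalised Cox would be a cheap improvement

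*Protocol*

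**What the plan says.** The protocol's Aim 3 analysis (Data Analysis section) starts with the composite: "Enrollment hospital admission diagnosis, indicators of malnutrition, age, and randomization arm will be assessed in a multivariable Cox regression model". It then adds that "Cox regression models will also be built for correlates of mortality and correlates of re-admission individually". The word multivariable is attached to the composite model only.

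The SAP's Aim 3 table (Section 6) has rows for the composite, for re-hospitalization and for death. All three share one list of 11 correlates. It opens with "Child nutritional status • HIV status (child & mother) • Vaccination status • Abnormal discharge • Discharge diagnosis • Length of hospital admission" and continues through infection, resistance, feeding, socio-economic and caregiver variables. The covariates are arm and site, and the model for time to death is ordinary Cox. Elsewhere in Section 6 the SAP has site enter every model as indicators, and its baseline table lists four sites.

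The expected mortality comes from the protocol's Aim 1 sample-size text: "Combined with our expected fatality rate (2-15%), we expect the cumulative incidence of the combined endpoint to range from 22.5 to 45.5" percent. The Aim 3 power statement uses the 22.5% composite rate and 20% loss, and gives no figure for mortality alone. Neither document limits the number of terms, handles sparse levels or names a penalised method for this outcome.

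**The concern.** Ordinary Cox regression has no finite maximum-likelihood estimate for a covariate level in which nobody dies: the hazard ratio runs to 0 and has no usable interval. When deaths are few relative to the terms fitted, the estimates that do converge can lie far from 1 by chance.

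Aim 3 sets out to identify cofactors of mortality separately from those of re-admission. Its mortality table could therefore contain blank or meaningless entries, and large hazard ratios that mainly reflect how few deaths there were. The primary comparison of the arms is not affected.

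**Working it through.** **1. Reproduce the planning case.** The protocol plans on "Using the most conservative estimates of a hazard ratio of 0.70 and 22.5% prevalence of re-admission/death". Schoenfeld's formula with two-sided alpha 0.05, power 0.80 and 1:1 allocation gives 4 × (1.960 + 0.842)² / (ln 0.70)² = 247 events. Reading 22.5% as the overall rate, 247 / 0.225 = 1,098 children, against 1,100 stated. The SAP's interim figure also agrees: 1,400 × 0.225 / 2 = 157.5, against 157.

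**2. Deaths inside that case.** The protocol expects that "re-hospitalizations will occur in 20.5 to 30.5% of children enrolled in the study". The 22.5% is therefore 20.5% + 2% deaths.

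- 2% of 1,100 = 22; 2% of 1,120 (1,400 less 20%) = 22.4; 2% of 1,400 = 28.
- At the other end of the stated range, 15% of 1,400 = 210.

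**3. Terms if all correlates enter together.** The documents do not fix this, so these are possible codings:

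- One term per listed item, plus arm and three site indicators: 11 + 1 + 3 = 15.
- Splitting the HIV item (child, mother) and the caregiver item (education, nutrition): 17.
- Four diagnosis indicators instead of one, plus age from the protocol's list: 17 + 3 + 1 = 21.
- Nine diagnosis indicators, age not counted: 17 + 8 = 25.

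| Terms | Deaths per term, 22 to 28 deaths |
|---|---|
| 15 | 1.5 to 1.9 |
| 21 | 1.05 to 1.33 |
| 25 | 0.9 to 1.1 |

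**4. One correlate at a time.** If a level has prevalence p and no association with death, the chance that none of D deaths falls in it is (1 − p)^D. The prevalences are assumptions; the documents give none.

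| Mortality | Deaths | p = 2% | p = 5% |
|---|---|---|---|
| 2% | 22 to 28 | 0.98²² = 64% to 0.98²⁸ = 57% | 0.95²² = 32% to 0.95²⁸ = 24% |
| 8% | 88 to 112 | 0.98⁸⁸ = 17% to 0.98¹¹² = 10% | 0.95⁸⁸ = 1.1% to 0.95¹¹² = 0.3% |

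At 2% mortality a level with 10% prevalence is empty of deaths in 5-10% of trials. A Cox simulation at 2% mortality, with one correlate plus arm and site, agreed: about 58% of fits were non-finite at 2% prevalence and 25% at 5%. Firth estimates stayed finite.

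**5. Joint models, by simulation.** Ordinary Cox was fitted with no true effects and assumed prevalences, 150 datasets per scenario (60 at 15% mortality). The share of fits with at least one non-finite hazard ratio was:

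| Terms | 2% mortality | 8% | 15% |
|---|---|---|---|
| 15 | 32-48% | 0% | 0% |
| 21 | 60-61% | about 1% | 0% |
| 25 | about 95% | 26% | 12% |

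With 21 terms at 2% mortality, 57-63% of fits also showed a finite hazard ratio above 3 or below 1/3 for a covariate with no effect. The type I error per coefficient stayed at about 4%.

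**The case against.** The strongest reply is that 2% is the floor of the stated mortality range and was used to size the composite, not to forecast deaths. The figure of 22 also drops lost children entirely, whereas the SAP censors them at their last visit, so 28 is nearer what an actual analysis would see at 2%. With more deaths the problem largely goes away. All of this stands, and it is why the point is conditional on low mortality.

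A reader might infer that the protocol commits to a joint mortality model of at least 21 parameters. The documents do not say so. The SAP's separate column for arm and site fits correlates being examined one at a time, its baseline table is descriptive and does not set the Aim 3 coding, and 15-17 terms are possible even jointly. Separate entry does not remove the difficulty for rare levels, as step 4 shows.

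A reader might also infer that hazard ratios will certainly be infinite, or that spurious findings will multiply. Neither is supported. Non-finite estimates are likely at 2% mortality but not certain, and depend on prevalences that the documents do not give. Type I error was not inflated. The SAP also plans Benjamini-Hochberg adjustment for the secondary aims and treats secondary analyses as hypothesis-generating.

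Finally, a level with no deaths is easy to see and could simply be described. That is true, but the plan does not provide for it, and it would not help levels with only one or two deaths.

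**Conclusion.** The point holds as a cheap improvement to a secondary analysis. At the 2% mortality inside the planning case, ordinary Cox regression for time to death rests on about 22-28 deaths. That is roughly 1-2 per parameter if the correlates enter jointly. If they enter singly, there is a 57-64% chance of no finite estimate for a level with 2% prevalence, and 24-32% for one with 5%.

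The consequence is non-finite or exaggerated and very imprecise hazard ratios, not an excess of significant results. At 8% mortality or more the problem is small except for rare levels or a finely coded diagnosis variable. The conclusion rests on the 2% figure, on assumed prevalences, and on no association between level and death. The primary analysis and the Aim 3 analyses of the composite and of re-hospitalization are not in question.

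**What to change.** In the time-to-death row of the SAP's Aim 3 table, and correspondingly in the protocol's Aim 3 sentence on mortality, replace ordinary Cox regression with Firth-penalised Cox regression and profile penalised-likelihood intervals. Keep ordinary Cox regression for the composite and for re-hospitalization.

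The cost is SAP wording and a standard routine in software that the SAP already allows. Estimates shrink slightly toward 1; if deaths prove numerous, the results will be close to ordinary Cox. Penalisation adds no information, so intervals for rare levels will still be wide. Stratifying by site, merging diagnoses or setting a minimum number of deaths per level are matters of preference and are not needed for this change.

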**Azithromycin to prevent post-discharge morbidity
and mortality in Kenyan children**

Toto Bora Trial

NCT02414399

Statistical Analysis Plan Version 5.0 (May 29, 2020)

TABLE OF CONTENTS

SECTION 1. ADMINISTRATIVE INFORMATION	2
Title	2
Trial Registration	2
SAP Version	2
Protocol Version	2
SAP Revision History	2
SECTION 2. INTRODUCTION	3
Background and Rationale	3
Objectives.....	3
SECTION 3. STUDY METHODS	4
Trial Design	4
Randomization	4
Sample size	4
Framework.....	4
Statistical Interim Analysis and Stopping Guidance.....	5
Timing of Final Analysis	5
SECTION 4. STATISTICAL PRINCIPLES	6
Confidence Intervals and P values	6
Analysis Populations	7
SECTION 5. TRIAL POPULATION	7
Screening Data.....	7
Eligibility	7
Recruitment.....	7
Baseline Patient Characteristics	8
SECTION 6. ANALYSIS	10
Outcome Definitions.....	10
Analysis Methods	11
Missing Data.....	15
Harms.....	15
Statistical software	16
References	16

SECTION 1. ADMINISTRATIVE INFORMATION

Title: Statistical Analysis Plan for Azithromycin to prevent post-discharge morbidity and mortality in Kenyan children: a protocol for a randomized, double-blind, placebo-controlled trial (the Toto Bora trial).

Trial Registration: NCT02414399

SAP Version: 5.0 (29May2020)

Protocol Version: 12Dec2017

SAP Revision History

SAP Revision history Version (date)	Justification for each SAP revision	Timing of SAP in relation to interim analysisⁱ
1.0 (21-Nov-2015)	Original	Before
2.0 (15-Mar-2016)	The DSMC reviewed our SAP and made suggestions which were implemented in an updated version. These changes included: plans for checking proportional hazards assumption, explicit mentioning of informative censoring, and addressing missing data. Specified interim analysis stopping rules and alpha boundary for final analysis. Added statistical analysis plan of secondary aims.	Before
3.0 (24 Aug 2017)	Clarified the primary outcome definition to exclude re-hospitalizations that were a continuation of the management prescribed as part of the original hospitalization or that occur during enrollment procedures (therefore hospitalizations that likely started prior to the investigational product being administered). Added the definition of loss to follow-up and a shell-table demonstrating how this information would be reported in quarterly reports. Updated the shell table for how adverse events would be reported by categories AE's in terms of Grade as opposed to specific AE's.	Before
4.0 (27 Sep 2019)	Re-formatted the SAP to be consistent with published guidelines for SAP (as outlined in JAMA. 2017; 318(23):2337-2343). Incorporated changes that had been discussed (and documented) during DMSC discussions (inclusion of site in ITT model, specifying primary adherence measure)	After
5.0 ⁱⁱ (29 May 2020)	Clarified how adherence data would be handled among those missing adherence information captured by questionnaire. Defined hospitalization as overnight stay (not previously defined). Specified cause of death would be determined by clinical consensus and secondarily by verbal autopsy. Updated shell tables.	After

i. All study personnel (other than the trial statistician) were blinded during the interim-analysis which included data through 31Oct2018
ii. Updated prior to unblinding

Roles and responsibilities in SAP and Signatures:

Name	Trial Role	SAP Role	Signatures
[name]	Project Director	Writing	
[name]	Trial Statistician	Senior statistician responsible	
[name]	Primary Investigator	Chief investigator/clinical lead	

SECTION 2. INTRODUCTION

Background and Rationale

An estimated 3.5 million deaths occur annually in children less than 5 years of age in sub-Saharan Africa, approximately 70% of which are due to infectious causes.^[1] One-year mortality rates as high as 15% have been documented following hospital discharge in sub-Saharan Africa, a rate that is 8-fold higher than non-hospitalized children.^[2-4] Children being discharged from hospital in Africa may represent an accessible high-risk population in which to target interventions to reduce mortality.

A recent trial of mass drug administration of azithromycin reduced childhood mortality by half among children in Ethiopia in communities receiving the intervention.^[5, 6] However, concerns about the potential for the emergence of antimicrobial resistance, possible toxicity, and the feasibility of delivery are all barriers to community-wide distribution of antibiotics.

A short course of azithromycin given to children with recent severe illness being discharged from hospital may optimize benefit while reducing both individual and population level risks. Azithromycin may reduce post discharge morbidity and mortality through infection-related mechanisms such as treating undiagnosed, incompletely treated or nosocomial infections, or by protecting against new or recrudescent infections that occur during recovery. Azithromycin may also act through non-antimicrobial pathways by anti-inflammatory and/or immune-modulatory effects.

Objectives

Aim 1. To compare rates of **re-hospitalization and mortality** in the 6 months following hospital discharge among Kenyan children receiving 5-day azithromycin vs. placebo.

Hypothesis: The provision of a 5-day course of azithromycin provided at discharge will reduce hospital re-admission and death within the 6 months following discharge, as compared to placebo.

Aim 2a. To evaluate possible **mechanism(s)** by which azithromycin may affect morbidity and mortality, by comparing **reasons for re-hospitalization and prevalence of pathogen carriage** between the randomization arms.

Hypothesis: Children treated with azithromycin will experience fewer hospitalizations due to diarrhea, acute respiratory infection, and malnutrition, and will be less likely to have respiratory and gastrointestinal carriage of potentially pathogenic organisms, as compared to children treated with placebo in the 6 months following hospital discharge.

Aim 2b. To determine whether empiric administration of azithromycin at hospital discharge **increases risk of antimicrobial resistance** in commensal *Escherichia coli* (*E. coli*) and *Streptococcus pneumoniae* (*S. pneumoniae*) isolates from treated children and their household contacts.

*Hypothesis: Isolates of commensal *E. coli* and *S. pneumoniae* from children treated with azithromycin and their household contacts will have higher levels of macrolide and β -lactam resistance, compared to the placebo group, after 90 days of follow-up, but resistance in the 2 arms will be similar by 6 months.*

Aim 3. To identify **correlates and intermediate markers of post-discharge mortality and hospital readmission** among hospitalized Kenyan children.

Hypothesis: Children younger in age, with higher levels of bacterial pathogen carriage, immune dysfunction, and malnutrition will experience more frequent re-hospitalizations and deaths.

Aim 4. To determine the **cost-effectiveness** of post-discharge administration of a 5-day course of azithromycin in settings of varying antibiotic use, re-hospitalization rates, and mortality rates.

Hypothesis: The provision of a 5-day course of azithromycin provided at discharge is cost-effective in settings with moderate to high re-hospitalization and mortality rates and this cost-benefit is sensitive to modest changes in individual and community levels of drug resistance.

SECTION 3. STUDY METHODS

Trial Design

A 2-arm, double-blind, randomized clinical trial (RCT) comparing the efficacy of a 5-day course of azithromycin to placebo among Kenyan children aged 1-59 months.

Randomization

Block randomization (1:1) in random-sized blocks of no more than 10 stratified by site will be used. Primary randomization will include allocation to the contact cohorts at a ratio of 1:5 (resulting in 150 per treatment arm). Each subject will be assigned a patient identification (PID) number, and the randomization code linking each PID to the allocated treatment will be generated by a designated statistician and maintained by the University of Washington Research Pharmacy. Study participants, investigators (other than the statistician), the study staff, hospital clinicians and persons involved in data management or analysis will remain blinded to the allocation group during all data collection phases of the study.

Sample size

The total sample size required (1400 children) was calculated for the primary endpoint of time to death or hospital readmission within the 6-month post-discharge period, assuming an alpha level of 0.05, power of 0.80, a ratio of treatment to placebo random assignment of 1:1, and a cumulative incidence of 22.5% for the combined outcome of death or re-hospitalization among placebo-treated children. Further details of the sample size calculation are outlined in the protocol.

Framework

All hypotheses are tested for superiority.

Statistical Interim Analysis and Stopping Guidance

A single interim analysis for re-hospitalization-free survival will be performed using O'Brien-Fleming boundaries for benefit or harm when 50% of expected person time (350 child-years) has been accrued. Assuming 157 events will be available at half of the person-time accrual, a z-score critical value of 2.797, or p -value < 0.005 , from a Kaplan Meier log-rank test will determine the cut-off of statistical significance. A symmetric boundary will be used for benefit or harm. The DSMC will review this analysis and make a determination about continuing the study. Futility will not be a basis for stopping rules because of the trials' value in understanding mechanisms of post-discharge worsening and antibiotic resistance. Assuming the DSMC decides to continue the trial after the interim analysis, an alpha of 0.045 will be used as the statistical significance boundary at the final analysis for the primary hypothesis test.

Timing of Final Analysis

The first main report/ publication of the trial will be prepared for the primary aim when every enrolled child has completed their 6 month follow-up visit or is deemed lost to follow-up and all primary endpoint data has been cleaned (anticipated publication in September 2020).

Timing of Outcome Assessments

The schedule of study procedures is outlined in Table 1. Regularly scheduled visits include those at M0 (hospital discharge), M3, and M6. Participants are actively followed for 1 month following their missed visit. If a visit occurs after the one month window, relevant data will be ascertained when possible, but may not be included in the analysis (as described in Table 1). The start date/time for each participant is the date/time of randomization.

Table 1. Allowable windows for each outcome

Outcome	Visit Window
Death or re-hospitalization	Follow-up time censored 180 days after enrollment or at the time of the last follow-up visit (if < 180 days). Data collected (including vital status) from visits that occur beyond 180 days will be included but events and person-time will be censored at 180 days.
Cause specific hospitalization	Follow-up time censored 180 days after enrollment or at the time of the last follow-up visit (if < 180 days). Data collected (including vital status) from visits that occur beyond 180 days will be included but events and person-time will be censored at 180 days
Prevalence of Shigella , Salmonella , Campylobacter , Cryptosporidium , Giardia @ enrollment, day 90, and day 180	Visits that occur within 30-days on either side of 90-days (M3) and 180-days (M6) visits will be included. Therefore, visits occurring outside of 60-120 days post-enrollment for M3 and outside of 150-210 days post enrollment for M6 will be excluded from the primary analysis but included in sensitivity analyses.
Streptococcus pneumoniae (S. pneumoniae) prevalence @ enrollment, day 90, and day 180	Visits that occur within 30-days on either side of 90-days (M3) and 180-days (M6) visits will be included. Therefore, visits occurring outside of 60-120 days post-enrollment for M3 and outside of 150-210 days post enrollment for M6 will be excluded from the primary analysis but included in sensitivity analyses.
Prevalence of resistance to azithromycin in E.coli and S. pneumoniae and prevalence of ESBL-producing E.coli @ enrollment, day 90, and day 180	Visits that occur within 30-days on either side of 90-days (M3) and 180-days (M6) visits will be included. Therefore, visits occurring outside of 60-120 days post-enrollment for M3 and outside of 150-210 days post enrollment for M6 will be excluded from the primary analysis but included in sensitivity analyses.

SECTION 4. STATISTICAL PRINCIPLES

Confidence Intervals and P values

Level of statistical significance

All statistical tests will be 2-sided using a 5% significance level (alpha of 0.05). For the primary aim (aim 1), an alpha of 0.045 will be used for hypothesis tests that were part of the interim analysis to account for alpha spending.

Type I errors

We will not adjust the alpha for multiple testing in the primary aim. Instead we will clearly state primary and secondary analyses and interpret secondary analyses as hypothesis-generating rather than confirmatory. All secondary aims will be adjusted for multiple comparisons using the Benjamini and Hochberg method using a false discovery proportion of 0.05.

Confidence intervals to be reported

For the primary analysis of Aim 1, two-sided 95.5% confidence intervals will be used to account for the 0.045 alpha spent at the interim analysis. All other analyses will utilize two-sided 95% confidence intervals.

Adherence and Protocol Deviations

Definition of adherence to intervention and how this is assessed including extent of exposure

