Prescribed antibiotics at discharge			
Nutritional, HIV, and Vaccine Status			
Breastfeeding status (in first 6 months of life)			
Exclusively breastfed			
Partially breastfed			
Never Breastfed			
Unknown			
Stunted (HAZ < -2)			

Underweight (WAZ < -2)			
Acute Malnutrition			
Severe (WHZ < -3 or MUAC <11.5cm or edema)			
Moderate (-3 ≥ WHZ < -2 or 11.5 ≥ MUAC <12.5cm)			
HIV-status			
HIV- infected			
HIV-exposed, uninfected			
HIV-exposed, unknown infection status			
HIV status unknown			
Received all age-appropriate vaccines			

SECTION 6. ANALYSIS

Outcome Definitions

Primary study end-points:

1. **Deaths** will be ascertained by study staff either through community health workers, hospital staff, or determined at follow-up visits. Date of death will be ascertained from the following (in order of prioritization): death certificate, hospital record, caregiver report
2. **Re-hospitalization** will be assessed by questionnaire at day 90 and 180 follow-up visits and medical record review. In cases when both sources are available, information from the medical record will be considered the gold standard. A hospitalization will be defined as an overnight stay, including situations where a child is admitted in the middle of the night (even if after midnight) and discharged the subsequent morning. Re-hospitalizations that are a continuation of management from the previous hospitalization (such as elective blood transfusion) or that occur during enrollment procedures, due to a clinical deterioration post-discharge, will be excluded from the analysis. To operationalize these exclusions, we will exclude re-hospitalizations that occur <2 hours after administration of the study medication and those re-hospitalizations that occur as a result of the child being advised to seek further care for a blood transfusion due to a lack of blood availability at the enrollment facility.
3. **Loss to follow-up** will be defined as non-attendance at both follow-up visits despite up to one month of active tracing and no clear evidence of death.
4. **Death or re-hospitalization** (combined) is the primary endpoint.

Secondary end-points:

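### The SAP's placebo-arm event rate of 22.5% and the protocol's hazard ratio of 0.70 do not together give 80% power at 1,100 evaluable children; they give about 74%.

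*SAP*

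**What the plan says.** - SAP, Section 3, Sample size: 1,400 children, alpha 0.05, power 0.80, 1:1 allocation and "a cumulative incidence of 22.5% for the combined outcome of death or re-hospitalization among placebo-treated children". No effect size or formula is given; the reader is sent to the protocol.
- Protocol, Sample Size, Aim 1: "Using the most conservative estimates of a hazard ratio of 0.70 and 22.5% prevalence of re-admission/death, we need to enroll 1100 children" (550 per arm). No arm is named for the 22.5%. Another 300 children are added "to account for possible loss to follow-up, resulting in a total planned enrollment of 1400 children, or 700 per treatment group".
- The same paragraph describes the wider exercise: "we calculated sample sizes using estimates of reduction in risk ranging from 30-50% with the cumulative incidence range of 22.5 to 45.5" percent, and the authors "found the sample size required ranged from 90 to 550 children per treatment arm".
- SAP, Section 3, Statistical Interim Analysis: "Assuming 157 events will be available at half of the person-time accrual".
- SAP, Table 1, on the primary endpoint: "Follow-up time censored 180 days after enrollment or at the time of the last follow-up visit". SAP, Section 6, on loss to follow-up: it "will be defined as non-attendance at both follow-up visits despite up to one month of active tracing and no clear evidence of death".

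**The concern.** The SAP's cross-reference obliges the reader to combine its event rate with the protocol's hazard ratio. A log-rank calculation depends on the number of events in both arms together. If 22.5% is the placebo rate, an effective treatment lowers the rate in the other arm, so fewer events occur than 22.5% of all children and more children are needed. The 1,100 appears to leave this out. The SAP alone cannot show it, because it gives no effect size.

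At stake is the planned-power statement, which readers use when they weigh a null or borderline result. The analysis itself is not affected.

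**Working it through.** **Inputs.** HR 0.70, 22.5%, alpha 0.05, power 0.80 and 1:1 allocation (Protocol, Sample Size, Aim 1); two-sided tests (SAP, Section 4); 22.5% in placebo (SAP, Section 3); 20% loss (Protocol, Sample Size, Aims 1 and 3). Neither document names a formula, so two standard log-rank formulas are used.

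**Events needed**
- Schoenfeld: 4 × (1.960 + 0.842)² / (ln 0.70)² = 246.8.
- Freedman: (1.960 + 0.842)² × (1.70/0.30)² = 252.0.

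**Reproducing the protocol's 1,100 (22.5% over both arms)**
- 246.8 / 0.225 = 1,097; 252.0 / 0.225 = 1,120. Both agree with 1,100.

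**Using the SAP's wording (22.5% in placebo)**
- Azithromycin rate under proportional hazards: 1 − 0.775^0.70 = 16.3%.
- Average over arms: (22.5% + 16.3%) / 2 = 19.4%.
- Children needed: 246.8 / 0.1942 = 1,271; 252.0 / 0.1942 = 1,298. This is 16 to 18% more than 1,100.

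**Power with placebo 22.5% and HR 0.70**, from Φ(√E/2 × |ln 0.70| − 1.960), where E is the number of events:

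| Situation | Events | Power |
|---|---|---|
| 1,100 evaluable | 213.6 | 74.1% |
| 1,400 enrolled, 20% with no follow-up (1,120 children) | 217.5 | 74.9% |
| 1,400, 20% seen to M3 only, constant hazard | 246.2 | 79.9% |
| Same, 60% of the cumulative hazard before M3 (assumed) | 251.6 | 80.7% |
| Same, 75% before M3 (assumed) | 259.4 | 81.9% |
| 1,400, no loss | 271.9 | 83.7% |

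Freedman values are about 1 point lower. At the SAP's final alpha of 0.045, the first two rows and the last become 72.6%, 73.4% and 82.5%.

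If loss means no follow-up at all, 80% power at alpha 0.05 requires loss of at most 1 − 246.8/271.9 = 9.2%.

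**Other figures in the documents**
- The low end of the protocol's range, 90 per arm, corresponds to HR 0.50 and 45.5%. Events needed are 65.3 (Schoenfeld) or 70.6 (Freedman). With 45.5% in placebo, azithromycin is 1 − 0.545^0.50 = 26.2% and the mean 35.8%, giving 91 or 99 per arm. With 45.5% over both arms it is 72 or 78. So 90 fits a placebo rate, while 550 at HR 0.70 fits a both-arm rate.
- Interim events: 700 × 22.5% = 157.5, which is the stated 157. With placebo 22.5% and HR 0.70, the like-for-like count is 700 × 19.42% = 136.
- Risk-ratio reading: 22.5% to 15.75% is HR ln(0.8425)/ln(0.775) = 0.672. This gives 521 per arm (Schoenfeld), 535 (Freedman), 532 (two proportions) or 561 (with continuity correction).

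**The case against.** **The effect may have been a risk ratio.** The protocol does speak of risk reductions of 30 to 50%. A 30% reduction from 22.5% in placebo gives 521 to 561 per arm, which is compatible with 550 and would leave the SAP correct as worded. It cannot be ruled out as the source. It does not remove the problem, because the protocol states a hazard ratio of 0.70 for a time-to-event endpoint. Its failure to reproduce 90 per arm (63 to 76) is not decisive, since the both-arm reading misses 90 as well.

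**The SAP attaches 80% to 1,400 children, not 1,100.** With no loss, 1,400 do give 83.7%. But the extra 300 were added for loss, and they do not restore 80% if the planned 20% contribute nothing.

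**The 75% is a worst case.** This stands. It needs every child in the 20% to yield no follow-up and no event. The SAP's definition of loss points that way, but a child seen only at M3 is not lost under it and contributes up to that visit. The protocol also provides telephone contact, household tracing and weekly monitoring of admissions. Its Background puts the highest mortality risk in the first 30 days, so the constant-hazard figure for partial follow-up may be slightly low.

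**A reader might infer that the 157 events prove a both-arm rate.** They do not. A count under no treatment effect, with both arms at the placebo rate, is also 700 × 22.5%, and that is a natural basis beside an O'Brien-Fleming boundary.

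**A reader might also infer that the protocol's 1,100 is an arithmetic error, or that the trial is shown to be underpowered.** Neither is supported. The 1,100 follows from a both-arm 22.5%. That rate is also the floor of the protocol's expected range of 22.5 to 45.5%, and a higher rate would raise power.

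**Conclusion.** The SAP's statement is wrong as written when it is read with the protocol to which it refers. A placebo rate of 22.5% with HR 0.70 needs 1,271 to 1,298 evaluable children and gives about 74% power at 1,100. At 1,400 enrolled the range is about 75% (20% with no follow-up) to 84% (no loss). If the 20% are seen to M3 only, it is about 80% under a constant hazard and 81 to 82% if 60 to 75% of the hazard falls before M3.

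This rests on HR 0.70, proportional hazards, two-sided alpha 0.05 and log-rank formulas; the early-hazard shares are assumptions. Which arm the designers meant is not established, because the documents' own figures do not follow one convention. Severity is minor: the planned-power statement is affected, and N, model, alpha and the 2.797 boundary are not.

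**What to change.** 1. Check the original sample-size calculation first, whichever reading seems likelier.
2. In SAP Section 3, Sample size, state the hazard ratio, the formula and the arm or arms to which 22.5% refers.
   - If it was the both-arm rate, replace the words that tie it to placebo.
   - If it is the placebo rate with HR 0.70, restate power as about 74% at 1,100 evaluable and about 75 to 84% at 1,400 enrolled, depending on loss. Mark this as conditional on HR 0.70 and, for partial follow-up, on the assumed hazard shape. Label any azithromycin-arm rate, such as 16.3%, as derived and not as an original assumption.
   - If the source shows a risk ratio, say so and give the formula.
3. In the interim section, label 157 as 700 children × 22.5% with the same rate in both arms (no treatment effect, or a both-arm rate). Add that placebo 22.5% with HR 0.70 would give about 136.

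The cost is a sentence or two, one clause and a look at the source calculation. No children are added and no analysis changes. If the placebo reading is confirmed, the stated power becomes a range with a less favourable lower end.
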